15. FINANCIAL AND OTHER COMPETING INTERESTS

At the time of writing the protocol, not all sites and personnel had been identified. Information on financial and other competing interests (if any) will be collected and documented in the Trial Master File (TMF).

16. INSURANCE AND INDEMNITY

The University of Birmingham has in place Clinical Trials indemnity coverage for this trial which provides cover to the University for harm, which comes about through the University's, or its staff's, negligence in relation to the design or management of the trial.

The risk of the trial is no greater than the risk of the usual clinical care. Responsibility for the participants at health facilities remains with the organisation responsible for the clinical facility and it is therefore indemnified through their normal arrangements.

17. PUBLICATION POLICY

A meeting will be held after the end of the trial to allow discussion of the main results among the collaborators prior to publication. Results of the formative phase, pilot, trial, process evaluation and health economic evaluations will be submitted as publications in peer-reviewed journals.

The success of E-MOTIVE depends on the collaboration of a large number of healthcare providers across several countries. For this reason, all publications arising from this work will be attributed to the “E-MOTIVE Collaborative Group”, with the writing committee and order approved by the ITMG.

Any secondary publications and presentations prepared by Investigators must be reviewed and approved by the ITMG. Manuscripts must be submitted to the ITMG in a timely fashion and in advance of being submitted for publication, to allow time for review and resolution of any outstanding issues. The ITMG are also obliged, by the terms of our contract to notify the funder (Bill & Melinda Gates Foundation) before submitting any publications. Authors must acknowledge that the trial was performed with the support of The University of Birmingham and funding from the Bill & Melinda Gates Foundation (including relevant acknowledgment text that will be provided by the ITMG).

Site investigators may access the full dataset if a formal request describing the plans of the analysis is approved by the ITMG. Individual countries will be allowed to publish their efficacy results, however the publication of efficacy results from the pooled analysis will take precedence over efficacy result publications of individual countries, unless the ITMG decides otherwise.

Appendix A

Modification of the Pakistan study design: Protocol for an E-MOTIVE before-and-after (implementation) study design

Rationale for the modification of the Pakistan study design

Pakistan was added as a participating country (8 main trial and 2 adaptive cycle sites) in September 2022 to provide South Asian representation in the main E-MOTIVE trial. At this time, the other 78 hospitals in the four African countries (Tanzania, Kenya, South Africa, and Nigeria) had already completed the baseline phase of the trial and commenced the post-randomisation phase. The Data Monitoring Committee (DMC) met on 24-Jan-2023 and observed that the pre-specified total study sample size had been achieved from the four African countries, therefore the trial data should be published without waiting for Pakistan to contribute data. This recommendation was subsequently ratified by the Trial Steering Committee (TSC) on 22-Feb-2023. It was unanimously agreed that there was no good scientific reason for the final analysis to be delayed, and that there was an ethical obligation to make the results available at the earliest, especially given that some of the settings across the world continue to see a high rate of PPH and maternal deaths. The African sites completed data collection on 03-Mar-2023. The final results, with data analysed from the four African countries showed that early (E) detection of postpartum haemorrhage and use of bundled treatment (MOTIVE) led to a lower risk of the primary outcome, that is a **60% reduction in the composite outcome (severe PPH, laparotomy for bleeding, or maternal death from bleeding)** in the E-MOTIVE arm compared to the arm that received usual care (published in NEJM on 09-May-2023).

Publication link: <https://www.nejm.org/doi/full/10.1056/NEJMoa2303966>

Given the above result from the African setting, the study design in Pakistan will now be adapted to a 'before-and-after' study to test the implementation of E-MOTIVE in a South Asian setting.

Aim

To study the key implementation (process outcomes) of E-MOTIVE in Pakistan (as a representation of the South Asian setting)

Methods

Design: This is a before-and-after study design. The baseline data that was collected at the 8 sites (all sites followed usual care) as a part of the main E-MOTIVE trial will be used to represent the 'before' phase of the study.

Setting: Eight secondary-level health facilities across Pakistan

All the 8 health facilities that completed a 5 to 6-month baseline period (until 31-Mar-2023) in which they were following usual care with dissemination of the current guidelines, will enter a 2-month transition (allowing two months for full implementation and embedding of E-MOTIVE). Following this, all 8 sites will implement E-MOTIVE for 3-months. Mixed methods work along with baseline-and-implementation phase healthcare provider observations will be conducted (Figure A1).

Key implementation outcomes:

Co-primary:

1. PPH detection [women who objectively had PPH (source-verified blood loss ≥ 500 mL after weighing the drape) and were diagnosed with PPH by the birth attendants divided by the total number of women who objectively had PPH (source verified blood loss ≥ 500 mL after weighing the drape)] **AND**
2. Compliance with MOTIVE bundle (women who objectively had PPH and were treated with the PPH bundle following a diagnosis of PPH by the birth attendants divided by the total number of women who objectively had PPH (blood loss ≥ 500 mL after weighing of the drape)

Secondary:

1. PPH treatment (women diagnosed with PPH by the birth attendants divided by the total of women having a vaginal birth in the health facility)
2. Bundle usage (women treated with the PPH bundle following a diagnosis of PPH by the birth attendants divided by the total of women having a vaginal birth in the health facility)
3. Bundle usage for PPH (with the following numerator and denominator: women treated with the PPH bundle following a diagnosis of PPH by the birth attendant divided by the total of women diagnosed with PPH by the birth attendants)
4. Uterine massage
5. Oxytocin use
6. Misoprostol use
7. TXA use
8. Intravenous fluids use
9. Examination of the genital tract
10. Number of women receiving any treatment uterotonic
11. Number of women requiring additional treatment interventions (not responding to the MOTIVE bundle).

Sample size

The power for the sample size calculated below is based on the two primary implementation outcomes (these will be the co-primary outcomes for this study) from the baseline data (PPH detection and adherence to MOTIVE bundle). Assuming eight health facilities in Pakistan, an average of 1,100 women per cluster would give an expected number of 1,000 women in the baseline phase with PPH and 500 women in the post-randomisation phase with PPH. The study will have $>90\%$ power to detect a change from 50% to 90% in the co-primary outcomes, after accounting for clustering (ICC of 0.25), cluster size variation ($cv = 0.5$) and adjusting the alpha level for the co-primary outcomes ($\alpha = 0.025$).

Analysis

This will remain the same as per the analysis of implementation outcomes in the main protocol (as described above).

[figure not shown]

Figure A1. Timeline depicting the baseline, transition and implementation phase for E-MOTIVE 'before-and-after' design in Pakistan along with process evaluation and healthcare provider observations

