The primary composite outcome (severe PPH, postpartum laparotomy for bleeding, and maternal mortality from bleeding) will be considered significant at the 5% level, and effect sizes and 95% CIs will be reported. Treatment effect measures with confidence intervals will be presented for the individual components of the primary composite (severe PPH, postpartum laparotomy for bleeding, and maternal mortality from bleeding), but it is not expected that there will be sufficient power to make definitive conclusions about any of them.

Results on secondary clinical and implementation outcomes (listed in section 6.2), will be interpreted with caution. To this end, treatment effect measures with confidence intervals will be presented as supporting evidence only.

All analysis will be carried out using Stata.

Subgroup Analyses

Tests for statistical heterogeneity (e.g., by including the treatment group by subgroup interaction parameter in the regression model) will be performed prior to any examination of effect estimate within subgroups. The subgroup analyses will be performed on the primary and key secondary implementation outcomes only.

Planned subgroup analyses include A) *Population subgroups*: age (three levels categorised by tertiles of the distribution), previous birth (none vs any), type of pregnancy (singleton vs multiple), gestational age (term vs preterm), type of birth (e.g. spontaneous versus assisted), risk factors for

PPH (diagnosis of preeclampsia, induction or augmentation of labour, previous caesarean, previous postpartum haemorrhage, antepartum haemorrhage, episiotomy, vaginal tears, retained placenta), baseline period PPH rate (low vs high PPH rate as objectively diagnosed by blood collection drape using data from the baseline period), country, number of vaginal births (above median vs below median as calculated using data from the baseline period); and B) *Intervention subgroups*: compliance with the E-MOTIVE intervention (defined as a minimum of administration of oxytocic drugs, TXA and IV fluids for objectively diagnosed PPHs; over the median and below the median; and time since intervention exposure (defined as number of months since cluster began post-randomisation phase).

Missing Data

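### Appendix A powers two co-primary outcomes at alpha 0.025, but the analysis it points to contains no such test and no success rule

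*Protocol*

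**What the plan says.** Protocol Appendix A describes Pakistan as a before-and-after study in eight facilities that all move from usual care to E-MOTIVE. Under its key implementation outcomes it lists PPH detection and compliance with the MOTIVE bundle as co-primary, joined by a capitalised AND.

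The sample size paragraph takes eight facilities averaging 1,100 women each, which leads to "an expected number of 1,000 women in the baseline phase with PPH and 500 women in the post-randomisation phase with PPH". Its claim is more than 90% "power to detect a change from 50% to 90% in the co-primary outcomes". The calculation uses an ICC of 0.25 and a cluster-size cv of 0.5. For multiplicity it works by "adjusting the alpha level for the co-primary outcomes", here to 0.025.

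The Analysis paragraph is a single sentence: "This will remain the same as per the analysis of implementation outcomes in the main protocol".

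In the main protocol, section 6.2 lists these two outcomes as key secondary implementation outcomes. Section 11.2 asks for caution in reading the outcomes of section 6.2 and says that "treatment effect measures with confidence intervals will be presented as supporting evidence only". Only the primary composite is judged at a stated level, 5%.

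The SAP does not fill the gap. Its section 4.1 covers Kenya, Nigeria, South Africa and Tanzania only. Section 5.1 reserves p-values for the primary outcome, with 95% intervals for the rest, and section 5.2 makes no multiplicity correction.

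**The concern.** A power statement describes a particular test at a particular level. Here the test is at 0.025 for each of two co-primary outcomes. The analysis to which the reader is sent has no test of these outcomes, no 0.025 level and no 97.5% interval. It also gives them a supporting role, which is at odds with calling them co-primary.

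The second gap is the success rule. Whether one outcome suffices or both are needed decides the correct alpha, the interval level and which power matters. Appendix A does not say. If one outcome improved clearly and the other did not, the result could be read as success or failure after the data were seen. These are the only primary outcomes of the Pakistan study, so its conclusion would have no pre-specified basis.

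**Working it through.** **1. The passages side by side**

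| Element | Appendix A, outcomes and sample size | Analysis referred to (section 11.2) |
|---|---|---|
| Status of the two outcomes | Co-primary | Secondary, supporting evidence |
| Level | 0.025 each | None stated for these outcomes |
| Interval level matching 0.025 | Not stated | Not stated |
| Success rule | Not stated | Not stated |

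**2. What the alpha split implies**

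- If either outcome can give success: 0.025 + 0.025 = 0.05, an exact Bonferroni split. With independent tests the familywise error is 1 − 0.975² = 0.0494; with no split it would be 1 − 0.95² = 0.0975.
- If both must succeed: 0.05 each already keeps the error at or below 0.05. Using 0.025 each caps it at 0.025, which is conservative.
- Matching intervals at 0.025 are 97.5% intervals, wider than 95% intervals by 2.241/1.960 = 1.14.

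**3. The stated power**

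Inputs from Appendix A: 8 facilities; 1,000 women with PPH before and 500 after, so m = 125 and 62.5 per facility; 50% to 90%; ICC 0.25; cv 0.5; alpha 0.025. Assumptions, because Appendix A does not give them: two-sided alpha, and the CAC, shown over a range.

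Design effect = 1 + ((1 + cv²)m − 1) × ICC:

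- before: 1 + (1.25 × 125 − 1) × 0.25 = 39.81
- after: 1 + (1.25 × 62.5 − 1) × 0.25 = 20.28

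Variance of the difference with independent phases: 0.25 × 39.81/1000 + 0.09 × 20.28/500 = 0.01360, so SE = 0.1166 and 0.4/0.1166 = 3.43.

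The same facilities are measured twice, so subtract 2 × CAC × ICC × √(0.25 × 0.09) × (1 + cv²)/8 = CAC × 0.01172.

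Power (normal) = Φ(0.4/SE − 2.241). At CAC 0 this is Φ(3.43 − 2.24) = 88.3%. At CAC 0.5 the variance is 0.00774, SE = 0.0880, and Φ(4.55 − 2.24) = 98.9%. With eight facilities a paired t reference on 7 df is more cautious; its power comes from the non-central t with the same ratio.

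| CAC | Normal | t, 7 df |
|---|---|---|
| 0 | 88.3% | 71.2% |
| 0.07 | 90.3% | 74.0% |
| 0.3 | 95.9% | 84.0% |
| 0.44 | 98.3% | 90.1% |
| 0.5 | 98.9% | 92.4% |
| 0.8 | >99.9% | 99.6% |

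The claim of more than 90% is reproduced from a CAC of about 0.07 (normal) or 0.44 (t).

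**The case against.** **The cross-reference may import only the model.** Appendix A expressly makes the two outcomes co-primary, so the deferring sentence can be read as carrying over the regression method and not the secondary status. Section 11.2 does not forbid tests of them, and the p-value restriction in the SAP does not reach Pakistan. An interval around a change as large as 50% to 90% would also be informative. This is a fair reading, and it rules out saying that the study cannot support a conclusion. It still leaves Appendix A without a test level, an interval level or a success criterion.

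**A reader might infer that AND makes the split wrong.** The documents do not support this. The word joins two items in a list of outcomes and is not a stated success rule, while 0.025 is the correct split for an either-outcome claim. Even under a both-outcome rule the split only costs power; it does not inflate error.

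**A reader might infer that the study is underpowered.** Taking 2p − 1 as the lower bound for success on both outcomes at CAC 0 (normal approximation) gives 77% at 0.025 and 86% at 0.05. Those figures need no correlation at all between phases in the same eight facilities, and nothing in the documents supports that. The main protocol considers a CAC of 0.95 to 1.0, with estimates of 0.97 and 0.99, although for a different outcome and setting. The two outcomes should also be positively related, because compliance is counted only after a diagnosis.

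**The wording change does not settle everything in that sentence.** The main model separates period from exposure through concurrent control facilities, and it omits a small-sample correction because about 70 facilities are expected. With eight facilities that all switch, period and exposure coincide. That objection stands, but it is a separate matter.

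**Conclusion.** The point holds as a mismatch between design and analysis. Appendix A powers each co-primary outcome at 0.025, and the analysis it invokes delivers no such test, no matching interval and no rule for success. This rests on the text alone.

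The stated power is not shown to be wrong. It depends on a CAC that Appendix A does not give: it falls just short under the normal approximation when the phases are taken as uncorrelated, and is met at moderate values under either reference distribution. These figures assume two-sided alpha. If 0.025 is one-sided, the normal-approximation power at CAC 0 is 92.9%.

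This should be corrected, because the study's only primary conclusion depends on it. The evidence does not show an inflated error rate or an inadequate sample.

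**What to change.** In Appendix A:

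1. State that the supporting-evidence rule of section 11.2 does not apply to the two co-primary outcomes.
2. Make the inference match the stated alpha: test each outcome at two-sided 0.025, report 97.5% intervals, and state that success on either outcome supports a claim about that outcome.
3. If the intention is that both must succeed, say so. Test each at two-sided 0.05 with 95% intervals, and restate the power for both jointly.
4. In either case, name the CAC and the reference distribution behind the claim of more than 90%.

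The cost is a few sentences in Appendix A and a restated power figure. Data collection and sample size do not change.

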and risk differences. We will use marginal standardisation to obtain the risk difference and risk ratio. Under a constrained baseline analysis, each observation has a binary indicator for time – indicating whether the observation was made during the baseline phase or the post-randomisation phase (which represents the change in the control arm over time) – and a binary indicator for treatment – indicating whether the observation was allocated to the usual care or E-MOTIVE (which represents the treatment effect). The constrained part of the model assumes no differences at baseline as is appropriate under a randomised design. This approach is recommended in cluster randomised trials with a baseline assessment of outcome.¹⁸ No small sample correction will be used as there are expected to be in the region of 70 health facilities in the analysis and the mixed model is expected to have appropriate estimation of the standard errors in this situation.¹⁹ Clustering will be allowed for in all analyses through the use of random effects. Recent developments in the methodological literature for the design and analysis of multiple-period cluster randomised trials suggest that a simple exchangeable correlation structure is not sufficient to depict the correlation structure in multiple-period cluster randomised trials.^{15,16} We will explore including a random cluster by period interaction in addition to a random cluster effect to allow for the decay in correlation between observations made in the same cluster, but at different time periods. If models with complex correlation structures do not converge, we will fit models with a simpler correlation structure. Other secondary outcomes will be modelled similarly, using appropriate link and distribution function in the generalised linear mixed model family.

The primary analysis will be unadjusted, except for factors used in the randomisation method (number of vaginal births per health facility, country, and quality of oxytocin per health facility during the baseline phase). As a sensitivity analysis, we will perform a propensity score (PS) based method – the direct PS adjustment as recommended by Leyrat et al²⁰ [Leyrat 2013]. Under this method, the PS is obtained by fitting a multivariable logistic model with potential confounders (age; parity; multiple pregnancy; mode of birth; and birth weight). The potential confounders have been proposed by the E-MOTIVE TMG following a consensus meeting.

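### Appendix A applies to 8 Pakistani facilities an analysis whose waiver of a small-sample correction rests on about 70, so the co-primary intervals come out too narrow unless facilities are almost perfectly stable over time

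*Protocol*

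**What the plan says.** Appendix A turns the Pakistan part of the trial into a single-group study: "This is a before-and-after study design". Eight facilities contribute usual-care baseline data, pass through a two-month transition, and then all use E-MOTIVE for three months. PPH detection and bundle compliance become co-primary, with alpha set at 0.025. The analysis section refers back to the main protocol: "This will remain the same as per the analysis of implementation outcomes in the main protocol (as described above".

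The text it points to is section 11.2, which specifies:

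- **Model.** A mixed-effect logistic model with constrained baseline analysis, in which "each observation has a binary indicator for time" and a second one for treatment.
- **Small-sample correction.** "No small sample correction will be used as there are expected to be in the region of 70 health facilities in the analysis".
- **Other outcomes.** "Other secondary outcomes will be modelled similarly".
- **Fallback.** "If models with complex correlation structures do not converge, we will fit models with a simpler correlation structure".
- **Covariates.** "The primary analysis will be unadjusted, except for factors used in the randomisation method".
- **Status of secondary outcomes.** "treatment effect measures with confidence intervals will be presented as supporting evidence only".

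The SAP covers Kenya, Nigeria, South Africa and Tanzania only. Its section 7.4 repeats the waiver for those countries. Its section 7.10 applies a between-within correction with a t-distribution to cluster-level subgroups.

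**The concern.** The waiver has a reason attached, and the reason is absent in Pakistan. Appendix A adopts the analysis without exception and offers no other justification. An analyst who follows the text would compare the before/after estimate with a normal cut-off, although the information on change comes from only 8 facilities. The resulting intervals for the two co-primary outcomes would be too narrow and the error rate too high.

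Two lesser problems come through the same cross-reference. First, the model cannot be fitted as written: every facility is unexposed before and exposed after, so the period and treatment indicators are the same variable. The constraint of no baseline difference between groups also has nothing to act on. Second, section 11.2 treats these outcomes as supporting evidence, whereas Appendix A makes them co-primary at 0.025 and gives no interval level to match.

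**Working it through.** **Inputs.** Appendix A gives 8 facilities, 1,000 women with PPH before and 500 after (1,000/8 = 125 and 500/8 = 62.5 per facility), ICC 0.25, cv 0.5, a change from 50% to 90%, and alpha 0.025. It does not state whether alpha is two-sided; two-sided is assumed here, as in section 11.1. It gives no CAC, so a range is shown. Section 11.1 considers 0.95 to 1.0, with estimates of 0.97 and 0.99, but these come from a different outcome in a different trial.

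**Step 1: the plan's own power figure.**

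- Design effect per period, 1 + ((1 + cv²)m − 1) × ICC: 1 + (1.25 × 125 − 1) × 0.25 = 39.81 before; 1 + (1.25 × 62.5 − 1) × 0.25 = 20.28 after.
- Variances: 0.25 × 39.81/1,000 = 0.00995; 0.09 × 20.28/500 = 0.00365.
- Covariance from using the same facilities: 1.25 × CAC × 0.25 × √(0.25 × 0.09)/8 = 0.00586 × CAC.
- SE = √(0.00995 + 0.00365 − 2 × 0.00586 × CAC). At CAC 0.95 this is 0.0497.

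| CAC | Power, normal cut-off | Power, t on 7 df |
|---|---|---|
| 0 | 88% | 71% |
| 0.25 | 95% | 82% |
| 0.44 | 98% | 90% |
| 0.5 | 99% | 92% |
| 0.8 | >99.9% | 99.6% |

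The stated figure of more than 90% reproduces. With the correction it still holds for a CAC of about 0.45 or more.

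**Step 2: size of the waiver's effect, analytically.** The two-sided 0.025 normal cut-off is 2.241. Its two-sided tail probability is 6.0% on t with 7 df, and 2.8% on 70 df. So the waiver is nearly harmless at about 70 facilities and more than doubles the error at 8. If 0.025 is one-sided, the cut-off is 1.960 and the error on 7 df is 4.5%.

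**Step 3: the mixed model itself, by simulation under no change.** Settings: 8 facilities, the PPH counts above, cv 0.5, prevalence 50% in both periods, ICC 0.25, facility and facility-by-period effects, maximum likelihood, model-based SE, cut-off 2.241. There were 4,000 linear runs per CAC (Monte Carlo SE 0.2 to 0.4 points) and 1,500 logistic runs (0.4 to 0.7 points).

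| CAC | Linear mixed model | Logistic mixed model |
|---|---|---|
| 0.8 | 7.9% | 7.5% |
| 0.95 | 6.7% | 7.7% |
| 0.97 | 5.1% | not run |
| 0.99 | 4.0% | 3.3% |
| 1.0 | 2.1% | 2.9% |

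Nominal is 2.5%. A paired t analysis of the 8 facility changes on 7 df stays at 1.9% to 2.5% throughout. As a further check, a cluster-robust logistic contrast with a normal cut-off gives 7.3% to 8.1% with 8 facilities (CAC 0.5 to 0.95), against 2.5% to 3.2% with 78. A t reference on 7 df brings the 8-facility figure down to 3.1% to 3.3%.

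**Step 4: interval width.** The t cut-off on 7 df is 2.841, and 2.841/2.241 = 1.27. At CAC 0.95 and a change from 50% to 90%, the half-width goes from 2.241 × 4.97 = 11.1 to 2.841 × 4.97 = 14.1 percentage points. These widths depend on the variance model: with a logit-scale variance of 1.723 and the CAC applied on that scale, they are about 14.3 and 18.2. The ratio is the same.

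**The case against.** **The carry-over is inferred.** Appendix A does not mention a small-sample correction. The waiver sits in the primary-outcome text of section 11.2, is tied to about 70 facilities, and reaches Pakistan through two general cross-references. One could say that it lapses at 8. That would still leave no rule for the co-primary analysis, and the literal text says the analysis is unchanged. Section 11.2 is a brief outline that defers detail to a SAP, but the SAP supplied does not cover Pakistan.

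**The inflation depends on the CAC.** This stands. Within the protocol's own range of 0.95 to 1.0, the error falls from about 7% to nominal, and the 6.0% is a t tail, not the mixed model's error. CAC 0.8 lies outside that range, but no document gives a value for these outcomes in Pakistan.

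**The fallback to a simpler correlation structure.** A reader might infer far worse inflation here. Fitting the facility-only model in every run does give 41% at CAC 0.8 and 17% at 0.95. But the protocol uses it only after non-convergence, whose probability is unknown. If it is used only when the facility-by-period variance is estimated at effectively zero (2%, 21%, 53% and 71% of runs at CAC 0.8, 0.95, 0.99 and 1.0), overall error is 7.0%, 7.4%, 3.7% and 1.8%, much as for the full model. The documents do not support the larger figures as an expected error rate.

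**Other readings that go too far.** A paired t analysis need not become the main analysis: it weights facilities equally and gives no risk ratio, which section 11.2 asks for. The randomisation covariates lose their rationale, and country is constant, but facility size and oxytocin quality could still be used as covariates.

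**Co-primary rule.** Appendix A joins the two outcomes with AND. If both must succeed, alpha need not be split. The plan nevertheless sets 0.025, and its intervals should match the level it states.

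**Conclusion.** The point holds for the validity of the co-primary intervals and tests. Followed as written, Appendix A uses a waiver whose only reason does not apply, and the error at a nominal 2.5% is about 7% at CAC 0.8 to 0.95, about 4% at 0.99 and near nominal at 1.0. This rests on a two-sided alpha, the ICC and cv in Appendix A, and a CAC that the documents do not give.

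A reader might infer that the power claim fails or that the trial's main result is in doubt. Neither follows. The power claim survives correction at a CAC of about 0.45 or more, a change as large as 50% to 90% would very probably be detected either way, and the randomised comparison in the four African countries does not use this analysis. The practical gain is correct coverage, and a correct error rate if the change is smaller than planned. It is worth fixing because the remedy is wording only.

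**What to change.** Replace the analysis sentence in Appendix A with:

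> Each co-primary outcome will be analysed with a mixed-effect logistic model with one before/after term and facility and facility-by-period random effects, reporting risk ratio and risk difference by marginal standardisation. A small-sample correction (t reference with between-within degrees of freedom, 7 df) will be used, with 97.5% intervals to match the alpha of 0.025. The waiver of a small-sample correction in section 11.2 does not apply. A paired t analysis of the 8 within-facility changes (7 df) will be reported as a check and will replace the mixed model if the model with facility-by-period effects does not converge; the facility-only model will not be used. The change includes any time trend.

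The 7 df are the 8 within-facility changes less one estimated mean. They should be named, because the rule in SAP section 7.10 (clusters minus parameters) would give 8 − 2 = 6 with an intercept and one term. The 97.5% level assumes that 0.025 is two-sided, which Appendix A should state.

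**Cost.** No design change and no new data. Intervals are about 27% wider. Power for small changes falls: for 50% to 65%, from 95% to 82% at CAC 0.95 (paired calculation). The correction is somewhat conservative if the CAC is close to 1: in the linear simulation, maximum likelihood with t on 7 df has an error of 3.2% at CAC 0.8 but 0.5% at 1.0. If the paired analysis has to replace the model, the result is a facility-average change without a risk ratio.
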